	3- Time elapsed till final restoration performed	Stopwatch	Continuous outcome measured in minutes

(S) Study design: Randomized controlled.

(T) Time of follow up:6 months.

8. Trial design:

Randomized controlled trial (R.C.T).

III. Methods

A) Participants, interventions & outcomes:

9. Study settings:

This study will be carried out on patients attending the out-patient clinic in Pediatric Dentistry and Dental Public Health Department-faculty of Dentistry, Cairo University, Egypt.

The procedure will be carried out by postgraduate student [name], B.D.S(2014)-Pharos University in Alexandria (PUA) and without an assistant.

10. Eligibility criteria:

Inclusion criteria:

- Children:

- 1- Aged 4 to 7, in good general health and medically free.
- 2- Cooperative patients who will comply to follow ups.
- 3- Parents provided with written informed consent.

- Teeth:

- 1- Bilaterally Carious vital primary molars with reversible pulpitis.
- 2- Restorable teeth with no more than 1/3 of root resorption.

Exclusion criteria:

- Children:

- 1- Children with medical, physical, or mental conditions.
- 2- Unable to attend follow up visits.

- Teeth:

- 1- Primary molars with any congenital anomalies.
- 2- Previously accessed teeth.
- 3- At operative procedure, haemorrhage control is unachievable after pulpotomy.

11. Interventions

The principal investigator will carry out all treatment procedures, using the split mouth technique, meaning that both groups (I & II) will be in the same patient.

For both interventions:

1. Informed consent from participating parents.
2. Baseline records photographs, percussion test, periapical radiograph, and personal data collection (Appendix 1: Diagnostic chart).
3. Allocation (concealed by withdrawing a sealed opaque envelope containing eight times folded paper containing the type of dressing material that will be used then writing patient name and ID on it and will be opened after performing the access cavity).
4. Diagnostic chart with personal, medical, and dental history will be filled (Appendix 1: Diagnostic chart).
5. Clinical examination will be performed to assess the clinical inclusion criteria. (Pulpal and periapical diagnosis is established after clinical examination).
6. Preoperative and Postoperative photographs will be taken.

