7. The radiographic examination will be performed by taking periapical x-ray using (parallel technique) through machine to assess the inclusion criteria. The preoperative radiograph will serve as a reference for the follow-up radiographs. Standardization of the technique to avoid any distortion in the vertical dimension and to provide reproducible images using x-ray holding device.
8. Preoperative and postoperative radiograph will be taken by parallel technique using XCP film holder (Super Bite, Hawe Neos Dental SA, Switzerland).
9. Administration of inferior alveolar nerve block (Septodont, Scandonest® 2% L Mepivacaine HCl. 2% and Levonordefrin 1:20,000 Injection, U.S.P.) at the side of the affected tooth.
10. Application of rubber dam for isolation, then a standardized pulpotomy procedure will be performed using a large sterile round end bur in a high-speed handpiece with copious irrigation, a sharp spoon excavator will remove pulpal tissues to the orifice level. Hemostasis will be achieved by the application of a wet cotton pellet to achieve complete hemostasis.
11. Children will then be allocated into either one of the groups alternatively depending on the pulpotomy medicament used as follows:
Group I (Experimental group) collagen based pulpotomy.
Group II (Control group) Biodentine pulpotomy.

Group I (Experimental group) collagen based Pulpotomy:

1. Collagen based pulpotomy will be applied (sterile medicated collagen particles, Biofil-AB, Eucare Pharmaceuticals Pvt. Ltd, Chennai, India) according to the manufacturer's instructions and gently placed over the pulp stumps to a thickness of 2 mm.

Group II (Control group) Biodentine pulpotomy:

1. Biodentine (Septodont, Saint-Maur-des-Fossés, France) will be applied according to the manufacturer's instructions and placed over the radicular pulp with the help of a suitable sterile amalgam carrier. Gentle condensation of the mix will be done in the pulp chamber with a moistened cotton pellet.

12. For both groups;

The rest of the pulp chamber will be filled with glass ionomer cement.

Tooth will then be restored with stainless steel crown (3M ESPE, St Paul, MN, U.S.A.).

12. Outcomes:

Primary outcome:

Absence of periapical radiolucency and internal/ external root resorption (Binary outcome detected with periapical x-ray by Parallel technique using XCP film holder (Super Bite, Hawe Neos DentalSA, Switzerland).

Secondary outcome:

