1- Survival rate (absence of any complication or complementary treatment) in terms of:

1-Absence of spontaneous pain. (Binary outcome measured with direct questioning to the patient).

2-Absence of swelling. (Binary outcome measured visually by intraoral/extraoral examination).

2- Time elapsed till final restoration performed.

13. Participant timeline:

Patients will be diagnosed to determine whether they are eligible for the inclusion criteria of this study or not.

Eligible patients will then start their treatment on the same visit.

	STUDY PERIOD					
	Enrolment	Allocation	Treatment visit	Post-treatment	Close-out	
TIMEPOINT	-t1	0	0	T1 (3m)	T2 (6m)	
ENROLMENT:						
Eligibility screen and patient selection	X					
Informed consent from participating pts	X					
Allocation (concealed in closed white envelop)	X					
INTERVENTIONS:						
The pulpotomy procedure (gaining access to the pulp)		X				
Allocation of the patient to one of the treatments groups (open the closed white envelope)		X				
Application of pulp dressing material (collagen and Biodentine)			X			
Final restoration			X			
ASSESSMENTS:						
baseline variables	1- photographs	X		X	X	X
	2- percussion test	X		X	X	X

	3- preoperative periapical radiograph	X				
	4- personal data	X				
outcome variables	Calculation of time-elapsed till final restoration			X		
	Questioning the patient about the absence of spontaneous pain	X			X	X
	Visual examination of patient to check the absence of sinus or Swelling	X			X	X
	Periapical radiograph to check the absence of periapical radiolucency, internal/ external root resorption	X		X	X	X

14. Sample size:

Sample size will be calculated.

15. Recruitment:

Patients attending the out-patient clinic in the pediatric dentistry department- Cairo University, having bilateral carious lower molars will be carefully assessed for eligibility to participate in our study by one of the main investigators [name], then a full explanation of the nature of our experiment and the importance of maintaining this primary tooth and restoring it for proper functions and the drawbacks of extracting it. Full mouth treatment will be offered for them.

B) Assignment of interventions:

16. Allocation:

16a. Random sequence generation (Randomization):

Teeth that will be included in the current trial will be randomly assigned one of the experimental groups using closed white envelopes (simple randomization 1:1 ratio).

a) Sequence generation:

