By shuffling the envelopes then selecting envelop for each patient upon their enrolment.

b) Allocation Concealment:

Using 8-time folded paper on which dressing material was written contained in the closed white envelope.

c) Implementation:

When a patient agrees to participate in the trial, an envelope will be drawn by one of the residents present at the clinic and name, telephone number and patient's ID will be written on it. Those selected envelopes will be opened at treatment visit after performing pulpotomy to choose which material should be used.

Randomization and allocation concealment will be performed by the co-supervisor to avoid selection bias.

17. Blinding:

The blinding is not possible (unfortunately) due to the nature of the trial.

Trial participants, outcome assessors and statistician will be blinded.

C)Data collection, management, and analysis:

18. Data collection methods

Baseline data collection

Plans for assessment and collection of outcomes will be at 3 and 6 months clinically (using visual examination, palpation, and percussion test with back of the mirror) and 0 and 6 months radiographically (using periapical radiograph) and will be done by two blinded assessors independently, and differences will be solved by consensus. To promote data quality, duplicate measurements by the same examiner (intra-examiner agreement) and training of assessors (inter-examiner agreement) will be done.

19. Data management:

Data will be recorded on a diagnostic chart for each patient separately and will be stored with follow up periapical radiographs.

20. Statistical methods:

Clinical and radiographic outcomes will be submitted for statistical analysis by the Statistical Package for Social Science (SPSS) program windows version 13. Results will be calculated using risk reduction (R.R.).

D) Data monitoring:

21. Monitoring

The study work results will be monitored regularly by the supervisors who will have full access to these interim results make the final decision to terminate the trial.

22. Harms

- **Bur breakage:** the bur will be replaced by a new one and treatment will be proceeded.
- **Perforation of pulpal wall or floor:** The tooth condition and size of perforation will be assessed whether the treatment will be to repair the perforation and treatment will be proceeded (the tooth will be removed from the trial) or the tooth will be extracted, and space maintainer will be performed

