- **No reported hypersensitivity from both tested materials.**
- **Failure of pulpotomy procedure:** retreatment of the tooth through partial pulpectomy and tooth will be removed from the trial.

23. Auditing

The study supervisors will regularly assess the trial process and documents. They will be involved in participant enrolment, consent, eligibility and allocation to study groups, adherence to trial interventions and policies to protect participants, including reporting of complications and their treatments. Clinical procedures will be performed under their supervision.

IV. Ethics and dissemination

24. Research ethics approval:

This protocol, the template and specific informed consent forms (local language and English versions) will be reviewed, approved, and agreed upon by the (Research Ethics Committee) will review all the nature of interventions and will have the right to modify the study methods.

25. Protocol amendments:

The Ethics Committee will be notified of any administrative changes or modifications of the protocol. Any required changes during the trial period for the patient's own interest that might affect the conduct of the study, including changes of the study objectives, study design, patient population, sample sizes, intervention procedures will require a formal amendment to the protocol. Such amendment will be agreed upon by the Council of the Department of Pediatric Dentistry, Faculty of Dentistry, Cairo University.

26. Informed consent:

The investigator will discuss the trial with the legal guardian of each participating child:

- Verbal permission will be taken orally from participating child.
- Written informed consent will be taken from the legal guardian of each participating child willing to participate in the trial. The consent form will be written in Arabic.

27. Confidentiality:

All data, information, participant's personal information, family history, social and medical history will be stored in the files assigned to each patient with limited access to a minimum number of individuals necessary for quality control, audit, and analysis.

28. Declaration of interest:

This study is a part of a master's degree in Pediatric Dentistry, Faculty of Dentistry, Cairo University. No financial conflict of interests is confirmed. The study is self-funded by the principal investigator.

29. Access to data:

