The investigator will be given access to data sets. All data sets will be password protected. To ensure confidentiality, data dispersed to project team members will be blinded of any identifying participant information.

30. post-trial care:

The investigator will offer full mouth treatment, post-operative care, and preventive measures to all participants.

31. Dissemination policy:

The Thesis defense will be done as the study is a part of the requirements for a master's degree in Pediatric Dentistry. Also, the results of the study will be published in Journals.

V. Appendices**Appendix 1: Chart filled for each patient in this trial:**

Patient name:

Patient ID:

Tested material:

Age:

sex:

Address:

Telephone:

Chief complain of the patient:

Pretreatment medications:

Participating tooth:

Date of material application:

Follow up		1ry outcomes assessment clinical assessment (survival rate)		2ry outcomes assessment Radiographic assessment			Final assessment “success or failure”
Time after	Date	1- Spontaneous pain	2- Swelling	3- Internal root resorption	4 - External root resorption	5- Periapical radiolucency	
3m	/ /20						
6m	/ /20						

VI. References:

- 1- izGuven SD. *Success Rates of Pulpotomies in Primary Molars Using Calcium SilicateBased Materials: A Randomized Control Trial. Biomed Res Int.* 2017;2017:7.
- 3- *Use of collagen as a biomaterial: An update - researchgate. (n.d.). Retrieved March 6, 2022, from* https://www.researchgate.net/publication/258204888_Use_of_collagen_as_a_biomaterial_An_update
- 5- J. Camilleri. “Hydration characteristics of biodentine and theracal used as pulp capping materials.” *Dent Mater.* 2014;30:709–715.

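### Section 22 takes a failed pulpotomy tooth out of the trial and does not say that it still counts as a failure in the analysis

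*Protocol*

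**What the plan says.** Section 22 (Harms) lists what is done when something goes wrong with a tooth. For failure of the pulpotomy the entry reads "retreatment of the tooth through partial pulpectomy and tooth will be removed from the trial". The entry on perforation uses the same removal language for a tooth whose perforation is repaired.

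Section 12 (Outcomes) makes the primary outcome radiographic: "Absence of periapical radiolucency and internal/ external root resorption". The first secondary outcome is "Survival rate (absence of any complication or complementary treatment", which is then specified in terms of spontaneous pain and swelling.

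Section 11 (Interventions) sets the design: "using the split mouth technique, meaning that both groups (I & II) will be in the same patient".

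Section 18 (Data collection methods) schedules clinical assessment at 3 and 6 months, but radiographs at "0 and 6 months radiographically (using periapical radiograph". The section 13 timeline has a row "Periapical radiograph to check the absence of periapical radiolucency, internal/ external root resorption" that is also marked at 3 months. The Appendix 1 chart has columns headed "2ry outcomes assessment Radiographic assessment" with rows for 3 and 6 months, and a final success/failure column for each row. (The chart labels these findings secondary; this point follows section 12.)

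Section 19 (Data management) says "Data will be recorded on a diagnostic chart for each patient separately". Section 20 (Statistical methods) names risk reduction as the measure and excludes no tooth.

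**The concern.** The trial compares two materials on the success of the pulpotomy. A rule that takes a tooth out because its pulpotomy failed selects on the outcome after randomisation. If the rule governs the data as well as the follow-up, the remaining teeth are a favourable selection, and each removal leaves an unmatched tooth in the same child.

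The primary outcome is the more exposed. Under section 18 a tooth retreated for pain or swelling at 3 months may have no follow-up film before it leaves. Even if its failure is charted, nothing says how it is scored radiographically.

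This goes beyond an analysis detail left to a later document. The protocol itself states the removal rule, and an analysis plan that kept these teeth would have to depart from its literal wording.

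**Working it through.** The protocol states no failure rate, sample size or power, so there is no figure to reproduce. The check has two parts.

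**1. The passages side by side**

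- Section 12 counts complementary treatment against survival, and retreatment by pulpectomy is naturally such treatment. Section 22 removes the same tooth. The conflict is partial, because section 12 then scores survival through pain and swelling.
- The Appendix 1 success/failure column could hold a 3-month failure. It is a blank field, with no rule carrying that failure into the 6-month result.
- A failure first found at 6 months has no later visit to lose. The exposure is therefore mainly failures found earlier.

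**2. What removal does under the literal reading**

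All inputs are assumed: failure risks f1 = 0.20 and f2 = 0.05, within-child correlation 0.3, and r = the share of failures removed before the 6-month visit, first taken as equal in both groups.

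*Only the failed tooth is lost:* apparent failure = f(1 − r)/(1 − fr). At r = 0.5: 0.10/0.90 = 0.111 and 0.025/0.975 = 0.026.

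*The whole pair is lost:* probability that both fail = f1·f2 + 0.3·√(f1(1 − f1)f2(1 − f2)) = 0.0100 + 0.0262 = 0.0362. First only is 0.1638, second only 0.0138, neither 0.7862. Pairs with two failures are kept with probability (1 − r)², discordant pairs with probability (1 − r), and the rest always. At r = 0.5 the kept total is 0.0090 + 0.0819 + 0.0069 + 0.7862 = 0.8840. The apparent risks are (0.0090 + 0.0819)/0.8840 = 0.103 and (0.0090 + 0.0069)/0.8840 = 0.018.

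| Removed | What is lost | Apparent failure | Difference (points) | Failure ratio |
|---|---|---|---|---|
| none | – | 20.0% vs 5.0% | 15.0 | 4.00 |
| 25% | tooth | 15.8% vs 3.8% | 12.0 | 4.16 |
| 25% | pair | 15.2% vs 3.3% | 12.0 | 4.66 |
| 50% | tooth | 11.1% vs 2.6% | 8.5 | 4.33 |
| 50% | pair | 10.3% vs 1.8% | 8.5 | 5.70 |
| 75% | tooth | 5.9% vs 1.3% | 4.6 | 4.53 |
| 75% | pair | 5.2% vs 0.7% | 4.5 | 7.55 |

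(Differences and ratios come from unrounded risks.) At an assumed 10% against 3%, the 7.0-point difference becomes 5.4, 3.7 and 1.9 at 25%, 50% and 75% removal.

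So with equal shares the absolute difference shrinks while the failure ratio moves away from 1. Whether the tooth or the pair is lost hardly matters for the difference but matters a good deal for the ratio.

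*Unequal shares, tooth only lost:*

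- 0% removed in the first group and 50% in the second: 20.0% vs 2.6%, so the difference grows to 17.4 points.
- 50% and 0%: 11.1% vs 5.0%, so it falls to 6.1 points.
- No true difference, 30 teeth per group, 4 failures in each, 2 collagen teeth removed: 2/28 = 7.1% vs 4/30 = 13.3%, a false advantage for collagen.

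*Equal failure and equal removal:* at 10% in both groups and r = 0.5, both show 4.5% if pairs are lost (5.3% at zero correlation). No false difference arises; only success is inflated.

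*Pairs:* at r = 0.5, pairs that lose a tooth number 0.0362 × 0.75 + (0.1638 + 0.0138) × 0.5 = 0.0271 + 0.0888 = 0.1159. The discordant share is 0.0888/0.1159 = 77%. Across correlations of 0 to 0.3 and both rate scenarios it is 77% to 96%. With equal shares the ratio of the two kinds of discordant pair stays at 0.1638/0.0138, about 11.8, so a paired comparison loses information but that ratio is not biased.

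**The case against.** The strongest reply is that section 22 is about harms and care, not analysis. It names no analysis set and does not say that data are discarded, and section 20 excludes no tooth. With the chart's success/failure column and the survival definition, the ordinary meaning may be: record the failure, retreat, stop follow-up. Denominators and carry-forward rules are commonly left to an analysis plan, which is not at hand. This stands as a plausible reading, and for survival it would avoid the bias. It is nowhere stated, however, and the neighbouring perforation entry uses the same words for a tooth that would naturally be excluded. It also leaves the radiographic score open.

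A second reply is that the failure meant could be operative, since the entry follows bur breakage and perforation and the section 13 table uses the term pulpotomy procedure for gaining access to the pulp. That is possible, but the research question uses the same term for the outcome being compared, and retreatment suggests a completed treatment.

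A reader might infer three stronger things. The first is that the protocol definitely discards failures; the Appendix 1 column prevents that conclusion. The second is that sections 12 and 22 flatly contradict each other; the restriction of survival to pain and swelling makes the conflict partial. The third is that removal necessarily pulls the comparison towards no difference; the unequal-share and ratio results above show otherwise.

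**Conclusion.** The point holds as a defect of wording that should be fixed. Section 22 states a removal rule triggered by the outcome, and nothing in the protocol keeps the tooth in the analysis or gives it a radiographic score. Under the literal reading, success rates are overstated in any group that loses failed teeth. The effect on the comparison depends on the removal share in each group and on the scale, and section 20's risk reduction could be absolute or relative. No fixed direction can be claimed.

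The size is unknown. Every figure above rests on assumed failure rates, correlation and removal shares, and the exposure is mainly failures found before the 6-month visit. Confidence is medium, because the milder reading may be what the investigators intend.

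**What to change.** Leave clinical care unchanged. In section 22, for failed pulpotomy only, replace the clause that removes the tooth with:

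> Study follow-up of the tooth may stop, but the tooth stays in the analysis in its randomised group, with its pair, and is counted as a failure from that visit onward.

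In section 12, add for the radiographic primary outcome:

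> Films taken up to failure are scored as read. A tooth retreated for failure with no later film is counted as a failure at 6 months. A sensitivity analysis uses recorded films only.

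As a related point, reconcile the radiograph timing in section 18 (0 and 6 months) with the section 13 table and Appendix 1, which both provide for 3 and 6 months.

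The cost is wording, with no extra patients. Reported success rates become less favourable. For teeth retreated on clinical grounds without a later film, the primary outcome becomes partly composite, which is why the recorded-film sensitivity analysis is needed. Scoring the last available film is an alternative; whichever rule is chosen should be fixed before outcomes are seen.

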2. Protocol Registration:

Protocol will be registered on clinicaltrials.org

3. Protocol version: 1

4. Funding:

The proposed clinical trial is self-funded.

5. Roles and responsibilities:

[name]: Department of Pediatric Dentistry and Dental Public Health Department, Faculty of Dentistry, Cairo University.

- Performs the clinical trial.
- Ensures participants' adherence throughout the trial.
- Collects the baseline data, results, interpretation and conclusions.
- Provide proper ancillary and post-trial care for all participants.
- Write the thesis.

Main supervisor & scientific advisor:

[name]. [name]: Professor of Pediatric Dentistry and Dental Public Health Department, Faculty of Dentistry, Cairo University.

- Monitors the whole process from the beginning of the trial and data collection.
- Assesses the final results and data collected from the study.
- Revises the thesis.

Co-supervisor:

[name]: Lecturer of Pediatric Dentistry and Dental Public Health Department, Faculty of Dentistry, Cairo University.

- Helps developing the protocol.
- Generates a random sequence to enroll the participants and undergoes proper allocation concealment, implementation, and access to the final data.
- Monitors the process of data collection and checks if there are any harms to the participants.
- Revises and helps in writing the thesis.

II. Introduction:

A) Background and rationale:

6.a. Research question:

In a child with cariously exposed vital primary molars, would it be better to use Collagen based pulpotomy or Biodentine based pulpotomy in terms of clinical and radiographic success of the pulpotomy procedure?

6.a. Statement of the problem:

Pulpotomy of vital primary molars is indicated when caries removal results in pulp exposure. Treatment approaches consist of devitalization using formocresol, preservation using ferric sulfate and regeneration of the remaining pulp tissue using mineral trioxide aggregate and recently Biodentine have been utilized. The ideal pulpotomy medicament would be biocompatible and bactericidal, in addition, to promoting the healing of the root pulp and be compatible with the physiological process of root resorption. (1)

Searching for more pulpotomy agents, Collagen, a protein that's present abundantly in humans, is an important component of connective tissues and performs multiple functions including wound healing.

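### The protection from selection bias claimed in section 16c is not assured: the preparer of the envelopes is not separated from entry decisions, and the allocation text conflicts

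*Protocol*

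**What the plan says.** **Who prepares the allocation.** Section 16c: "Randomization and allocation concealment will be performed by the co-supervisor to avoid selection bias". The co-supervisor's entry in section 5 goes further: "Generates a random sequence to enroll the participants and undergoes proper allocation concealment, implementation, and access to the final data".

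**Who has a hand in entry.** Section 23 (Auditing) begins: "The study supervisors will regularly assess the trial process and documents". It continues: "They will be involved in participant enrolment, consent, eligibility and allocation to study groups", and adds: "Clinical procedures will be performed under their supervision". Section 5 lists a main supervisor and a co-supervisor, and section 23 makes no exception for either. Section 15 says that patients "will be carefully assessed for eligibility to participate in our study by one of the main investigators". Section 11 says: "The principal investigator will carry out all treatment procedures, using the split mouth technique".

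**How the allocation is made.** Section 16 describes simple 1:1 randomization by shuffled envelopes, one chosen per patient. A clinic resident draws it once the patient has agreed and writes the patient's identifiers on it. Step 11 of section 11 reads: "Children will then be allocated into either one of the groups alternatively depending on the pulpotomy medicament used as follows".

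**Envelope and opening time.** Section 11 calls the envelope sealed and opaque; sections 13 and 16 call it closed and white. No serial number or log is mentioned. It is opened after the access cavity in section 11 (step 3) and after the pulpotomy in section 16c.

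**The concern.** Giving the sequence to a named person prevents selection bias only if that person takes no part in deciding what enters the trial, or if the mechanics keep the next allocation unknown to everyone. The protocol rests its claim on the first condition and then leaves it open in section 23. The second depends on the envelope procedure, which is described inconsistently and leaves no record by which its use could be checked.

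In a split-mouth trial the choice of children cannot by itself favour a material, because every child receives both. What can favour one is the assignment of the worse tooth of a pair to a particular material, or the exclusion of a tooth during the operation once its material is known. If that happened, the comparison of radiographic and clinical success would carry a bias that no later analysis could remove, because the allocation trail cannot be rebuilt.

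**Working it through.** The protocol gives no figure on this point, so the check is a comparison of its sections.

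1. **Roles.** Section 16c gives randomization and concealment to the co-supervisor. Section 23 involves the supervisors, as a group, in enrolment, consent, eligibility and allocation. The co-supervisor is one of the two supervisors in section 5. The overlap is in the text, although how far *involved* reaches is not stated.

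2. **Implementer.** Section 5 lists implementation among the co-supervisor's tasks; section 16c has a resident draw the envelope. The two fit if the co-supervisor merely oversees the draw, but the protocol does not say so.

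3. **Traceability.** Identifiers are written on the envelope after it is drawn. From then on it is tied to the patient. Before then, with no number and no log, an envelope could be set aside and another drawn without evidence.

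4. **Method.** Section 16 specifies shuffled envelopes. Step 11 of section 11 says *alternatively*. If that means one or the other, it is loose wording. If it means alternation, each allocation follows from the last and concealment is lost.

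5. **Unit.** Section 16a assigns teeth, the next paragraph selects one envelope per patient, and step 11 allocates children. The envelope names a dressing material, yet both materials go into the same child. No rule says which tooth the named material is for.

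6. **Opening time.** Uncontrollable haemorrhage after pulpotomy is an exclusion in section 10. Under step 3 of section 11 the envelope may be open before that judgement. Under section 16c, and in the order of steps 10 and 11, the judgement on the first tooth can come first. If one envelope settles both teeth and they are treated in turn, the second tooth's material is known before its own intraoperative judgements under either rule.

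7. **Size.** Let *d* be the excess failure rate of the worse tooth in a pair and *p* the probability that it goes to one given arm. The spurious difference between arms is p·d − (1 − p)·d = (2p − 1)·d. Fair randomization has p = 0.5 and gives zero. Assuming d = 10 percentage points, p = 0.60 gives (1.20 − 1) × 10 = 2 points and p = 0.75 gives (1.50 − 1) × 10 = 5 points. The protocol supplies neither *d* nor *p*, so these results show only how the bias would scale. They do not estimate it.

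**The case against.** The strongest reply is that the section 23 sentence stands under Auditing, after a statement about reviewing process and documents, and so describes oversight. Operational tasks are assigned elsewhere: eligibility to a main investigator (section 15), all treatment to the principal investigator (section 11), the draw to a resident (section 16c). Preparing envelopes also gives no foreknowledge if they are shuffled, sealed and opaque, drawn by someone else after agreement, labelled at once and opened only during the operation.

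Much of this stands, and it rules out two stronger readings that a reader might infer. The first is that the protection fails. The documents do not support it, because under the procedure as written the preparer does not know which envelope a child will get. The second is that the co-supervisor is present when individual teeth are judged. Supervision of procedures is stated, but nothing says that it is chairside or which supervisor gives it.

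Two smaller replies are also fair. Sealed and opaque does not contradict closed and white; the latter is a less complete description. And separating roles would not stop the operator from knowing the second tooth's material.

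The reply does not supply the missing separation. If *involved* means taking part, the preparer helps to decide entry; if it means audit, the preparer audits their own allocation. Nor does it settle the implementer, the missing numbering, *alternatively* or the opening time.

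**Conclusion.** The concern holds in limited form: the protection claimed in section 16c is not assured. The co-supervisor prepares and conceals the allocation and is not excepted from the group involved in enrolment, consent, eligibility and allocation. The text that should make this harmless conflicts on who implements, how allocation is made and when the envelope is opened, and it provides no numbering.

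The residual risk is at tooth level. Its size cannot be computed from the documents, and the 2 to 5 points above rest wholly on assumed inputs. The conclusion assumes that section 23 means both supervisors, as its plural suggests. The point about predictability applies only if *alternatively* is followed as alternation. Correction is worthwhile because it is nearly free before enrolment and impossible afterwards.

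**What to change.** - **Section 23:** exclude whoever prepares the envelopes from enrolment and eligibility decisions. General audit may remain.
- **Sections 5 and 16c:** name the resident as the person who issues envelopes, and limit the co-supervisor's task to generating the sequence and preparing the envelopes.
- **Sections 11, 13 and 16:** specify sealed opaque envelopes throughout, serially numbered after shuffling, used strictly in number order and entered in a log. Have each state which tooth (for example right or left) its material applies to, with the other material going to the paired tooth.
- **Section 11, step 11:** delete *alternatively* and refer to the envelope.
- **Sections 11 and 16c:** reconcile the opening time, and say how it stands to the haemorrhage judgement in section 10.

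These are changes of wording and need no added staff. The cost is slightly less involvement of the co-supervisor and a short log to keep. They do not prevent the operator from knowing the second tooth's material once the first envelope is open; logging every tooth excluded after opening, with the reason, would at least make such exclusions visible.
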